## **7.7 Preparation/Handling/Storage/Accountability**

The IP should be stored in a secure area according to local regulations. It is the responsibility of the Investigator to ensure that IP is only dispensed to study participants. The IP must be dispensed only from official study sites by authorized personnel according to local regulations.

The product storage manager should ensure that the study treatment is stored in accordance with the environmental conditions (temperature, light, and humidity) as determined by BMS. If concerns regarding the quality or appearance of the study treatment arise, the study treatment should not be dispensed, and study personnel must contact BMS immediately.

Study treatment not supplied by BMS will be stored in accordance with the package insert.

IP documentation (whether supplied by BMS or not) must be maintained that includes all processes required to ensure drug is accurately administered. This includes documentation of drug storage, administration and, as applicable, storage temperatures, reconstitution, and use of required processes (eg, required diluents, administration sets).

For study treatments not provided by BMS and obtained commercially by the site, storage should in accordance with the product label.

Storage facilities for controlled substances must be securely locked and substantially constructed, with restricted access to prevent theft or diversion, as applicable by local regulations.

Further guidance and information for final disposition of unused study treatment are provided in the Pharmacy Manual.

### **7.7.1 Retained Samples for Bioavailability/Bioequivalence**

Not applicable.

## **7.8 Treatment Compliance**

Not applicable.

## **7.9 Concomitant Therapy**

### **7.9.1 Prohibited and/or Restricted Treatments**

The following medications are prohibited during the study (unless utilized to treat a drug-related AE):

- Immunosuppressive agents.
- Immunosuppressive doses of systemic corticosteroids (except as stated in [Section 6.2](#)).
- Any concurrent anti-neoplastic therapy (ie, chemotherapy, immunotherapy, extensive, non-palliative radiation therapy, or standard or investigational agents for treatment of cancer). Palliative hormonal therapy will be permitted when indicated.
- Any botanical preparation (eg, herbal supplements or traditional Chinese medicines) intended to treat the disease under study or provide supportive care. Use of marijuana and its derivatives for treatment of symptoms related to cancer or cancer treatment are permitted if obtained by medical prescription or if its use (even without a medical prescription) has been legalized locally.
- Any live/attenuated vaccine (eg, varicella, zoster, yellow fever, rotavirus, oral polio and measles, mumps, rubella [MMR]) during treatment and until 100 days post last dose.
- Administration of investigational SARS-CoV-2 vaccines is not allowed during the study. Participants may receive authorized or approved SARS-CoV-2 vaccines while continuing on study treatment at the discretion of the investigator. See [Section 6.2 Exclusion Criteria](#).
- Treatment of active SARS-CoV-2 infections or high risk exposures, including use of investigational therapies, is allowed and should be discussed with the medical monitor.

### **7.9.2 Other Restrictions and Precautions**

Participants with a condition requiring systemic treatment with either corticosteroids ( $> 10$  mg daily prednisone equivalent) or other immunosuppressive medications within 14 days of randomization or treatment assignment are excluded. Inhaled or topical steroids, and adrenal replacement steroid doses  $> 10$  mg daily prednisone equivalent, are permitted in the absence of active autoimmune disease.

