  - i) Participants with advanced stage cutaneous melanoma who have received standard therapies with proven survival benefit including prior immunotherapy with an anti-PD-1 or anti-PD-L1 containing regimen and must have progressive or recurrent disease after prior PD-1/PD-L1 directed therapy. Participants must not have received prior anti-CTLA-4 therapy in the advanced or metastatic setting. Additionally, participants with cutaneous melanoma must have also been offered mutation-directed therapy, if indicated, that has proven survival benefit; if a participant refuses such therapy, it must be documented in the medical record. No more than 1 intervening therapy is allowed but not required between prior anti-PD-1/anti-PD-L1 containing

regimen and BMS-986218. No more than 70% of the randomized participants should have had progression of disease within a period of 6 months of start of therapy with anti-PD-1/PD-L1 agent. Only cutaneous melanoma is allowed. Mucosal and uveal/ocular melanomas are not allowed; melanoma with unknown primary site may be enrolled if the investigator determines mucosal and uveal/ocular primary sites are unlikely.

j) The BMS-986218 Cohort Expansion - Monotherapy (Part 2B):

- i) Participants must have received, and then progressed, relapsed, or been intolerant to at least 2 standard systemic therapies with proven survival benefit according to their tumor types in the advanced or metastatic setting, if available. If the participant refuses or is not eligible for these regimens, the reason must be documented in the medical record. Additionally, participants must have progressed or have recurrent disease after prior immunotherapy with anti-PD-1/anti-PD-L1 either by itself or in combination with other systemic therapy agents. No more than 1 intervening therapy is allowed but not required between prior anti-PD-1/anti-PD-L1 containing regimen and BMS-986218. Participants who have been intolerant to prior immunotherapy are excluded. Prior anti-CTLA4 therapy is allowed for no more than 20% of participants, and details of treatment (including dates, doses, and response) must be available.
  - (1) Lung/NSCLC (adenocarcinoma or squamous cell carcinoma); additionally, for NSCLC, all participants with adenocarcinoma must have known EGFR, ALK, and ROS-1 status. Participants with an activating EGFR mutation, ALK translocation, or ROS-1 mutation must have received appropriate inhibitor therapy.

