### 3) Medical History and Concurrent Diseases

- a) Participants with concomitant second malignancies (except adequately treated non-melanomatous skin cancers or in situ urothelial, breast, or cervical cancers) are excluded unless a complete remission was achieved at least 2 years prior to study entry, and no additional therapy is required or anticipated to be required during the study period.
- b) Participants with other active malignancy requiring concurrent intervention.
- c) Prior organ allograft.
- d) Toxicity (except for alopecia) related to prior anti-cancer therapy and/or surgery, unless the toxicity is either resolved, returned to baseline or Grade 1, or deemed irreversible.

- i) Any active neuropathy > Grade 2 (NCI Common Terminology Criteria for Adverse Events [CTCAE] v4.03).
- e) Participants with the following:
  - i) Active, known, or suspected autoimmune disease.
    - (1) Participants with well controlled asthma and/or mild allergic rhinitis (seasonal allergies) are eligible.
    - (2) Participants with the following disease conditions are also eligible:
      - a. Vitiligo.
      - b. Type 1 diabetes mellitus.
      - c. Residual hypothyroidism due to autoimmune condition only requiring hormone replacement.
      - d. Euthyroid participants with a history of Grave's disease (participants with suspected autoimmune thyroid disorders must be negative for thyroglobulin and thyroid peroxidase antibodies and thyroid stimulating immunoglobulin [Ig] prior to the first dose of study treatment).
      - e. Psoriasis not requiring systemic treatment, or conditions not expected to recur in the absence of an external trigger are permitted to enroll.
  - ii) History of life-threatening toxicity related to prior immune therapy or any toxicity that resulted in permanent discontinuation from prior immune therapy (eg, anti-CTLA-4 or anti-PD-1/PD-L1 treatment or any other Ab or drug specifically targeting T-cell co-stimulation or immune checkpoint pathways) except those that are unlikely to re-occur with standard countermeasures (eg, hormone replacement after adrenal crisis).
  - iii) Conditions requiring systemic treatment with either corticosteroids > 10 mg daily prednisone equivalents or other immunosuppressive medications within 14 days of study treatment administration, except for adrenal replacement steroid doses ≤ 10 mg daily prednisone equivalent in the absence of active autoimmune disease.

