### **7.9.3 Permitted Therapy**

Participants are permitted the use of the following treatments:

- Topical, ocular, intra-articular, intra-nasal, and inhalational corticosteroids.
- Adrenal replacement steroid doses  $\leq 10$  mg daily prednisone equivalent.
- A brief (less than 3 weeks) course of corticosteroids for prophylaxis (eg, contrast dye allergy) or for treatment of non-autoimmune conditions (eg, delayed-type hypersensitivity reaction caused by a contact allergen).
- Palliative hormonal therapy will be permitted when indicated.

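### Section 7.9.2 permits adrenal replacement steroids above 10 mg/day prednisone equivalent, but exclusion 6.2 3)e)iii) exempts, and Section 7.9.3 lists, only doses up to 10 mg/day

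*Combined protocol and SAP*

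**What the plan says.** Four provisions of the current protocol text bear on pre-existing adrenal replacement.

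- **Section 6.2, exclusion 3)e)iii).** The exclusion covers "Conditions requiring systemic treatment with either corticosteroids > 10 mg daily prednisone equivalents", or other immunosuppressants, within 14 days of study treatment, "except for adrenal replacement steroid doses ≤ 10 mg daily prednisone equivalent in the absence of active autoimmune disease".
- **Section 7.9.1.** Among prohibited medications it names "Immunosuppressive doses of systemic corticosteroids (except as stated in" Section 6.2). The whole list is lifted for drugs used to treat a drug-related adverse event.
- **Section 7.9.2.** It restates the exclusion above 10 mg/day, then adds that inhaled or topical steroids and "adrenal replacement steroid doses $> 10$ mg daily prednisone equivalent, are permitted in the absence of active autoimmune disease".
- **Section 7.9.3.** The list of permitted treatments includes "Adrenal replacement steroid doses $\leq 10$ mg daily prednisone equivalent".

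On the standing of the entry criteria, Section 6 grants no exceptions, the closing paragraph of Section 6.2 insists that every criterion be met, and Section 9 rules out waivers.

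**The concern.** The same dose limit points in opposite directions in sections that sites use side by side. Section 7.9.2 is not background text: it is worded as an entry rule, saying who is excluded and what is permitted. A coordinator who looks up steroids there finds express permission for a dose that the exclusion criterion rules out.

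The situation is foreseeable. Section 3.3 names adrenal insufficiency among the treatment-related events of ipilimumab or nivolumab, and exclusion 3)e)ii) makes an exception for toxicities that are "except those that are unlikely to re-occur with standard countermeasures (eg, hormone replacement after adrenal crisis"). Someone who passes 3)e)ii) on that ground must still meet 3)e)iii), where the 10 mg threshold decides.

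What is at stake is an avoidable eligibility deviation, or inconsistent entry decisions between sites, in a trial of immune-activating antibodies where background steroid dose is deliberately limited.

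**Working it through.** There is no sample size, power or error-rate figure to reproduce, so the check applies each provision literally, dose by dose. The case is pre-existing adrenal replacement, no active autoimmune disease, and no drug-related adverse event under treatment.

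| Daily dose (prednisone equivalent) | 6.2 3)e)iii) | 7.9.2 | 7.9.3 | Conflict at entry? |
|---|---|---|---|---|
| 5 mg | not excluded | not excluded, not named as permitted | listed | no |
| 10 mg | not excluded | not excluded, not named as permitted | listed | no |
| 15 mg | excluded | permitted | not listed | yes |
| 20 mg | excluded | permitted | not listed | yes |

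The conflict covers every dose above 10 mg/day and none at or below it.

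**Which sign is the mistake?** The 6.2 exclusion applies when the dose is > 10 mg. Its exception applies when the dose is ≤ 10 mg. No dose satisfies both, so the exception changes the outcome at no dose. It would do something only if it reached doses above 10 mg, which is what 7.9.2 says. Against that, two of the three places that state a replacement threshold say ≤ 10 mg. The count favours an error in 7.9.2, while the logic of the exception leaves open an error in 6.2 and 7.9.3. The text alone does not settle it.

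**After entry.** The contradiction is weaker here, for three reasons.

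1. Section 7.9.1 does not define an immunosuppressive dose, so it is not certain that replacement above 10 mg/day is caught by it.
2. Section 7.9.3 is not stated to be exhaustive, so absence from its list is not a prohibition.
3. Treatment of drug-related adverse events is exempt under 7.9.1, and Section 7.6.3.1 lets participants with drug-related endocrinopathy resume on physiologic hormone replacement with no dose limit in mg.

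**The case against.** The best reply is that the documents already say which text governs entry. Section 6 fixes eligibility without exceptions, and 7.9.1 sends steroid exceptions back to 6.2. Someone on 15 mg/day fails 6.2 whatever 7.9.2 says, so what remains looks like one mistyped sign in a concomitant-therapy paragraph, with no consequence for any population, endpoint or dose decision.

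Most of that stands. Section 6.2 does control entry, the affected group is narrow, and nothing statistical turns on it. But the controlling status of 6.2 is why 7.9.2 needs correcting: it grants in plain words what a criterion without waivers forbids.

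A reader might infer more than the documents support.

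- *That the error must lie in 7.9.2.* The inert exception in 6.2 prevents that certainty.
- *That the protocol contradicts itself equally during treatment.* The three points on post-entry use above stand against this.
- *That ineligible participants were enrolled, or that response estimates are distorted.* The documents show no such enrolment and give no frequency for replacement above 10 mg/day.

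**Conclusion.** The text is wrong as written, and the error is minor. At entry, pre-existing adrenal replacement above 10 mg/day prednisone equivalent without active autoimmune disease is excluded by 6.2 3)e)iii) and expressly permitted by 7.9.2. After entry the position is unclear rather than plainly contradictory. The conclusion rests on a literal reading of current, unredacted text and on 6.2 taking precedence for eligibility. Its size is the number of candidates on such replacement, which the documents do not give. No effect on objective response rate, power or error rates follows.

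**What to change.** The sponsor first confirms the intended threshold.

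**Default (replacement above 10 mg/day is not meant to be allowed).** In the adrenal replacement sentence of 7.9.2, change > 10 mg to ≤ 10 mg. Keep the condition on active autoimmune disease. It also governs the inhaled and topical steroids in that sentence, and the 7.9.3 entry for "Topical, ocular, intra-articular, intra-nasal, and inhalational corticosteroids" does not carry it. The cost is one sign at the next amendment, with no eligibility criterion changed. The 6.2 exception would still have no effect on dose, but all three places would agree.

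**Alternative (replacement above 10 mg/day is meant to be allowed).** Leave 7.9.2 and reword both 6.2 3)e)iii) and 7.9.3 to cover adrenal replacement including doses above 10 mg/day prednisone equivalent, provided there is no active autoimmune disease. The word *including* matters: simply reversing the sign in 7.9.3 would drop doses up to 10 mg/day from its permitted list. This costs two edits, one of which loosens an exclusion criterion, so the sponsor should also decide whether an upper limit is wanted.

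Neither route adds visits or data.

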### **7.9.3 Permitted Therapy**

Participants are permitted the use of the following treatments:

- Topical, ocular, intra-articular, intra-nasal, and inhalational corticosteroids.
- Adrenal replacement steroid doses  $\leq 10$  mg daily prednisone equivalent.
- A brief (less than 3 weeks) course of corticosteroids for prophylaxis (eg, contrast dye allergy) or for treatment of non-autoimmune conditions (eg, delayed-type hypersensitivity reaction caused by a contact allergen).
- Palliative hormonal therapy will be permitted when indicated.

#### **7.9.4 Palliative Radiation**

Palliative radiation for disease-related symptoms may be offered to all participants on the study after the DLT evaluation period. Limited radiation therapy to control symptoms from isolated lesions is permitted for participants who have Investigator-assessed clinical benefit following consultation with the BMS Medical Monitor or designee. Participants should not receive study treatment during radiation, as the potential for overlapping toxicities with radiotherapy and BMS-986218, ipilimumab, or BMS-986218 in combination with nivolumab is currently not known. Anecdotal data suggest that radiotherapy administered to participants while receiving nivolumab therapy is tolerable; however, because concurrent radiotherapy and immunotherapies in cancer have not been formally evaluated, in cases where palliative radiotherapy is required for a tumor lesion, BMS-986218, ipilimumab, and/or nivolumab should be withheld for at least 1 week before, during, and 2 weeks after radiation. Participants should be closely monitored for any potential toxicity during and after receiving radiotherapy, and AEs related to radiotherapy should resolve to Grade 1 prior to resuming study treatment. Participants who have received palliative local therapy will be documented as having had disease progression for the purpose of efficacy analyses.

Details of palliative radiotherapy should be documented in the source records and eCRF. Details in the source records should include dates of treatment, anatomic site, dose administered and fractionation schedule, and AEs. Symptoms requiring palliative radiotherapy should be evaluated for objective evidence of disease progression. Participants receiving palliative radiation of target lesions will have the evaluation of objective response rate (ORR) just prior to radiotherapy, but these participants will no longer be evaluable for the determination of response subsequent to the date palliative radiation occurs.

#### **7.9.5 Surgery**

Participants undergoing major surgery for any reason while on study should have BMS-986218, ipilimumab, and/or nivolumab held for at least 4 weeks after surgery, and these study treatments should not be resumed until wound healing has occurred and it is considered safe to do so in the assessment of the Investigator.

For participants who need to undergo surgery during the study, it is recommended to hold study treatment(s) for at least 2 weeks before (if elective or planned) and 3 weeks after surgery or until the participant recovers from the procedure, whichever is longer. Wound healing must be evaluated by surgeon prior to resuming study treatment. Prior to resuming study treatment, surgically related AEs should resolve to Grade 1 or baseline, and participants must meet relevant eligibility criteria as determined by the BMS Medical Monitor (or designee) in discussion with the Investigator.

#### **7.9.6 Imaging Restriction and Precautions**

It is the local imaging facility's responsibility to determine, based on participant attributes (eg, allergy history, diabetic history, and renal status), the appropriate imaging modality and contrast regimen for each participant. Imaging contraindications and contrast risks should be considered in this assessment. Participants with renal insufficiency should be assessed as to whether they should receive contrast and if so, what type and dose of contrast is appropriate.

Specific to MRI, participants with severe renal insufficiency (ie, estimated glomerular filtration rate < 30 mL/min/1.73 m^2) are at increased risk of nephrogenic systemic fibrosis. MRI contrast should not be given to this participant population. In addition, participants are excluded from MRI if they have tattoos, metallic implants, pacemakers, etc.

The ultimate decision to perform MRI in an individual participant in this study rests with the site radiologist, the Investigator, and the standards set by the local Ethics Committee.

## **7.10 Treatment After the End of the Study**

At the end of the study, BMS will not continue to provide BMS supplied study treatment to participants/Investigators unless BMS chooses to extend the study. The Investigator should ensure that the participant receives appropriate standard of care to treat the condition under study.

# **8 DISCONTINUATION CRITERIA**

## **8.1 Discontinuation from Study Treatment**

Participants MUST discontinue for any of the following reasons:

- Documented disease progression as defined by RECIST v1.1 ([Appendix 5](#)) or per PCWG 3 criteria for prostate ([Appendix 12](#)) unless participants meet criteria for treatment beyond progression ([Section 8.1.1](#)).
- Clinical deterioration while receiving active study therapy that, in the opinion of the Investigator, indicates that continued participation in the study is not in the best interest of the participant.
- Any drug-related AE occurring at any time that meets DLT criteria as outlined in [Section 7.6.1](#) will require permanent discontinuation. Exceptions to permanent discontinuation are listed in [Section 7.6.4](#).
- Participant's request to stop study treatment. Participants who request to discontinue study treatment will remain in the study and must continue to be followed for protocol-specified follow-up procedures. The only exception to this is when a participant specifically withdraws consent for any further contact with him/her or persons previously authorized by participant to provide this information.
- Any clinical AE, laboratory abnormality or intercurrent illness that, in the opinion of the Investigator, indicates that continued participation in the study is not in the best interest of the participant.
- Termination of the study by BMS.
- Loss of ability to freely provide consent through imprisonment or involuntarily incarceration for treatment of either a psychiatric or physical (eg, infectious disease) illness. (Note: Under specific circumstances, and only in countries where local regulations permit, a participant who has been imprisoned may be permitted to continue as a participant. Strict conditions apply and BMS approval is required.)
- Inability to comply with protocol.
- Discretion of the Investigator.
- Pregnancy.

- Individual participants with confirmed CR will be given the option to discontinue study therapy on a case-by-case basis after specific consultation and agreement between the Investigator and BMS Medical Monitor (or designee) in settings where benefit-risk justifies discontinuation of study therapy.
- Any event that leads to delay in dosing lasting > 8 weeks from the previous dose requires discontinuation, with the following exceptions:
  - Dosing delays for prolonged steroid tapers to manage drug-related AEs are allowed.
  - Dosing delays lasting > 8 weeks from the previous dose that occur for non-drug-related reasons may be allowed if approved by the BMS Medical Monitor (or designee).
- If a participant in any of the nivolumab/BMS-986218 combination arms meets criteria for discontinuation, because it is not possible to determine whether the event is related to both or 1 study treatment, the participant should discontinue both nivolumab and BMS-986218 and be taken off the treatment phase of the study.

Refer to the Schedule of Activities ([Section 2](#)) for data to be collected at the time of treatment discontinuation and follow-up and for any further evaluations that can be completed.

In the case of pregnancy, the investigator must immediately, within 24 hours of awareness of the pregnancy, notify the BMS Medical Monitor/designee of this event. In most cases, the study treatment will be permanently discontinued in an appropriate manner (eg, dose tapering if necessary, for participant safety). Refer to [Section 9.2.5](#) Pregnancy.

All participants who discontinue study treatment should comply with protocol-specified follow-up procedures, as outlined in Section 2. The only exception to this requirement is when a participant withdraws consent for all study procedures including post-treatment study follow-up or loses the ability to consent freely (ie, is imprisoned or involuntarily incarcerated for the treatment of either a psychiatric or physical illness).

If study treatment is discontinued prior to the participant's completion of the study, the reason for the discontinuation must be documented in the participant's medical records and entered on the appropriate CRF page.

